### 10.9.2 Amendment 2.0 (update from protocol version 2.0 to 3.0)

The amendment implements updates for clarification, updates reflecting the decision to perform SAR-CoV-2 viral genome sequencing for all subjects (and not just if triggered), and adaptations to the statistical analysis reflecting discussion of booster data analysis with the FDA which requires the exclusion of certain protocol deviations from the primary analysis and thereby makes the Per Protocol Set redundant.

### 10.9.3 Amendment 3.0 (update from protocol version 3.0 to 4.0)

This amendment implements three additional cohorts (Cohorts 7, 8, and 9) within Part C, comprising an additional ~410 subjects who:

- have received two or three doses of any authorized COVID-19 RNA-based vaccine, e.g., 30 µg BNT162b2 (Comirnaty) or the Moderna vaccine (Spikevax), and
- had a breakthrough SARS-CoV-2 infection from January 2022 on (limited to a period when there was a high prevalence of SARS-CoV-2 Omicron infections).

Subjects in Part C will receive either 30 µg of the monovalent BNT162b2 (B.1.1.529) as a third or fourth dose, 30 µg BNT162b2 as a third or fourth dose, or no vaccination within 3 months of Visit 1.

In addition, a third dose of the multivalent vaccine has been added for Cohort 6, Parts A and B comprising BNT162b2-naïve subjects, with planned visits at pre-Dose 3, 1-week post-Dose 3, and 1-month post-Dose 3.

For subjects who receive non-trial SARS-CoV-2 vaccinations, blood samples for humoral immunogenicity and T-cell and B-cell response assessments will not be collected, and they will be discontinued from the BNT162-17 trial.

The amendment also includes updates for clarification and an updated Table 8, which following the request of the IEC in Germany now includes information on the SARS-CoV-2 Omicron variant.

### 10.9.4 Amendment 4.0 (update from protocol version 4.0 to 5.0)

This update implements a change in eligibility criteria for Part C. Eligibility criteria were updated to correspond to the existing regulatory guidance, clarifying the required time

frame between the last dose of the COVID-19 RNA-based vaccine and first IMP dose. The two-month window between the documented SARS-CoV-2 infection and trial IMP administration was implemented to reduce heterogeneity in baseline VNT levels which may affect immune responses after trial vaccine administration. The mandatory NAAT test as a confirmation of prior SARS-CoV-2 infection was adjusted according to suggested updated algorithms for SARS-CoV-2 infection diagnostics.

In addition, based on the recent immunogenicity data from the BNT162b2 Omicron variant vaccine in the BNT162-16 trial, the sample size and expected GMR have been adjusted accordingly.

### **10.9.5 Amendment 5.0 (update from protocol version 5.0 to 6.0)**

This update implements a correction, specifically the insertion of Table 5.

### **10.9.6 Amendment 6.0 (update from protocol version 6.0 to 7.0)**

This amendment implements updates in response to FDA comments (dated 08 JUN 2023) and the decision to include additional immunogenicity analyses in the primary objectives and secondary objectives for COVID-19 vaccine-naïve subjects (Cohort 6) in Part B.

See the table below for a summary of the reasons for major changes compared to the previous version. Minor editorial changes, such as the correction of typing errors or formatting, are not specifically listed here. A redline draft showing all content updates is available upon request.

Section	Reason for change
All sections	The date and version number were updated.
All applicable sections	Updates to clarify that the original Omicron strain B.1.1.529 has since been renamed B.1.1.529.1 (known as Omicron BA.1), with the Omicron lineage having expanded into multiple sublineages. Notes were added in applicable sections.
Title page	The sponsors medical representative was updated. The document history was updated to reflect this update.
1 and 2.2	1 (Trial rationale) and 2.2 (Trial rationale) updated to reflect the current BNT162b2 authorization status. Updates to clarify that the original Omicron strain B.1.1.529 has since been renamed B.1.1.529.1 (known as Omicron BA.1), with the Omicron lineage having expanded into multiple sublineages. Updates to explain how the data from Part B of the trial will be used.
1 and 3	1 (Objectives and endpoints) and 3 (Objectives and endpoints) Updates for clarification, to reflect the additional immunogenicity analyses, and correction. This included the addition of two Primary objectives (Immunogenicity) and two secondary objectives for Part B.
1 and 4.1	1 (Trial design) and 4.1 (Overall design) Update to reflect addition of new analyses.
1.3	1.3 (Schedule of activities) Update of applicable table headers to reflect a change from "BNT162-naïve subjects" to "COVID-19 vaccine-naïve subjects"
ABBREVIATIONS/ TERMS	Updates to reflect updates elsewhere and addition of missing entries.
2.1.1	2.1.1 (Overview of the disease)

Section	Reason for change
	Updates to reflect the current disease status.
2.3.1	2.3.1 (Risk assessment) Updates to add data cutoff dates.
6.3	6.3 (Measures to minimize bias: randomization and blinding) Text updated for clarification.
8.3.4	8.3.4 Regulatory reporting requirements for SAEs) Text updated for clarify where to find reference safety information in the current BNT162 IB.
9.1	9.1 (Statistical hypotheses) Updates to reflect the additional immunogenicity analyses.
9.1.1	9.1.1 (GMT non-inferiority) Insertions to reflect the additional immunogenicity analyses.
9.1.2	9.1.2 (SR non-inferiority) Insertions to reflect the additional immunogenicity analyses.
9.1.3	9.1.3 (Multiplicity considerations) Insertions to reflect the additional immunogenicity analyses.
9.2.2	9.2.2 (Part B) Insertions to reflect the additional immunogenicity analyses.
9.4.3.1	9.4.3.1 (Geometric mean ratios) Insertions to reflect the additional immunogenicity analyses.
9.4.3.2	9.4.3.2 (Seroresponse) Insertions to reflect the additional immunogenicity analyses.
10.3.1.10	10.3.1.10 (Reporting of SAEs and AESIs) Updates for clarifications on the new e-mail addresses and fax number for safety reporting.
10.9.6	10.9.6 [Amendment 6.0 (update from protocol version 6.0 to 7.0)] Section added to summarize this update.

## 10.10 Data collection and management

The trial documentation must be adequate for the reconstruction of the trial.

### 10.10.1 Case report forms

CRFs will be completed through use of an electronic data capture (EDC) system. Trial site personnel will receive training and have access to a manual for appropriate CRF completion. The CRFs will be submitted electronically to the sponsor via the system and should be handled in accordance with instructions from the sponsor.

All CRFs should be completed by designated, trained trial site personnel. CRFs should be reviewed, verified, and then electronically signed and dated by the investigator or a designee.

At the end of the trial, the investigator will receive trial subject data for his/her trial site in a readable format that must be kept with the trial records. Acknowledgment of receipt of the trial subject data will be required.

### 10.10.2 Trial subject reported outcomes

Not applicable.

### **10.10.3 Data management**

The CRO (see the title page) will be responsible for data management of this trial, including quality checking of the data.

Data entered manually will be submitted to the sponsor through use of an EDC system, data extracts, and reports. Trial sites will be responsible for data entry into the EDC system. In the event of discrepant data, the data management service provider will request data clarification from the trial sites, which the trial sites will resolve electronically in the EDC system.

The data management service provider will produce a Trial Data Validation Specification document that describes the quality checking to be performed on the data. CRFs and correction documentation will be maintained in the EDC system's audit trail.

Central laboratory data will be sent directly to the data management service provider.

System backups for data stored by the sponsor and records retention for the trial data will be in accordance with regulatory requirements.

### **10.10.4 Investigator's Site File and the TMF**

The principal investigator or deputy is responsible for the filing of all essential documents in an ISF. The sponsor or a delegated CRO is responsible for the timely filing of all essential documents in the TMF. As applicable, these files must be available at monitoring visits and during audits or regulatory inspections.

After trial completion, the principal investigator or deputy must ensure that all source data and documentation related to the trial is recorded, handled, and stored in a way that allows its accurate reporting, interpretation, and verification. The principal investigator or deputy must take measures to prevent accidental or premature destruction of these documents.

The principal investigator or deputy must keep the ISF, the source data/documentation arising from the trial according to the prescribed record retention period in the country and/or according to the hospital policy, but at least until informed by the sponsor that the trial-related records are no longer required.

1 VERSION HISTORY

Table 1. Summary of changes

Version/ date	Associated protocol	Summary and rationale for changes
1/ 17 Jan 2022	Protocol V3.0, 05 Nov 2021	N/A
2/ 30 Jan 2023	Protocol V6.0, 04 Aug 2022	
The document is updated to align with the updates made in protocol version 6.0 (CTP V6 04Aug2022).
 
Also, the document is modified to align with regulatory requirements on presentation of summaries and analyses outputs.
 
Minor editorial changes, such as typing errors are not listed here.
 
Throughout the document:
 
 • Summaries and analysis for trial Part C is added. • “Systemic reactions” is changed to “systemic events.” • Where appropriate, “Study” meaning clinical study is changed to “Trial” meaning clinical trial. • Hyphens in “1 month” removed. • “mcg” is replaced with “µg”. • IgG and Biomarkers analysis are removed from the document. 
Section 2.1:
 
 • Description of objectives, estimands and endpoints for Part C of this trial are added. 
Section 2.2.1.3:
 
 • Trial design for Part C is added. 
Section 3.1.1:
 
 • The definition of “Last Dose” for each cohort is added.

Version/ date	Associated protocol	Summary and rationale for changes
		
Section 3.1.1.1:
 
 Onset day definition is modified to make it clear that reactogenicity events onset day will be computed separately for each IMP injection. Maximum duration description is modified to make it clear that reactogenicity events maximum duration computation will be computed separately for each IMP injection. 
Section 3.1.1.3:
 
 AE/SAE section is revised to align with CTP v6.0. 
Section 3.1.2:
 
 The primary immunogenicity endpoints for Part B of the trial are revised as per the CTP v6.0. The definition of seroresponse after immunization is revised for ease of derivation. 
Section 3.1.3:
 
 The primary immunogenicity endpoints for Part C are included as per the CTP v6.0. 
Section 3.2.1:
 
 The secondary immunogenicity endpoints for Part C are added as per the CTP v6.0. 
Section 3.3:
 
 Exploratory immunogenicity endpoints for Part-C added as per the CTP v6.0. In case an Exploratory endpoint is also a primary or secondary endpoint for any part of the study A, B or C then it would not be repeated in analysis. 
Section 3.3.1:
 
 Confirmed COVID-19 Cases and the handling of Surveillance Period are updated. 
Section 3.3.2:
 
 "Nucleocapsid-binding antibody seroconversion" and the Surveillance Period are updated.

Version/ date	Associated protocol	Summary and rationale for changes
		
Section 3.4:
 
 • Baseline value to use in the derivation of SR was modified for clarity. • A derivation for Baseline SARS-CoV-2 infection status was added. • The analysis visit handling for safety analysis and the protocol specified window for Immunogenicity and sensitivity analysis has been updated. 
Section 3.4.1:
 
 • The variable “Time at IMP dose 1 since dose 2 of BNT162b2 (days)” and “Childbearing potential” was added. 
Section 3.4.2:
 
 • The concomitant medication/procedure part is updated. 
Section 4:
 
 • To capture wrongly dosed subjects in the IPD table the analysis set used to generate this table was changed from “Safety set” to the “Screened Set”. • Immunogenicity per protocol analysis set was added in Table 8 of Analysis set. 
Section 5:
 
 • A sentence was added to make it clear that only reactogenicity events within 7 days will be reported in the analysis and summaries. 
Section 5.1.4.2 and 5.1.4.3:
 
 • Updated to reflect the objectives of updates as per CTP v6.0. 
Section 5.2:
 
 • “Data assessed after the vaccination with a non-trial vaccine” will not be part of statistical analysis.

Version/ date	Associated protocol	Summary and rationale for changes
		
Section 5.3:
 
 • A sentence was included to make it clear that missing binary and continuous data will be presented only if there is a non-zero count for at least one of the Cohorts. • For all trial parts, if no data is available to any of the Cohorts, then the output will show “No data to display”. 
Section 6.1.1.1:
 
 • This section was modified to clarify that local reactions recorded beyond 7 days will be excluded from the analysis. 
Section 6.1.1.3:
 
 • A summary table for solicited AE that continues longer than 7 days post vaccination or an SAE or an AE that fits the definition of a solicited AE but starts after Day 7 was included. 
Section 6.1.2:
 
 • Sensitivity Analysis will be done updated throughout all the subsections of this part. 
Section 6.2:
 
 • The presentation of the bar graphs updated to include LLOQ and ULOQ horizontal lines also color coding to differentiate data from subjects N-binding assessment for the respective visit, time point.
3/ 29 Jun 2023	Protocol V7.0, 28 Jun 2023	
Section 2.1, 3.1.2, 3.2.1, 5.1, 6.1.2, 6.2.2:
 
 • Add primary and secondary objectives, endpoints, hypotheses, and analyses and summaries for the new objectives in Protocol V7.0. 
Section 3.1.2
 
 • “Value above ULOQ will be set to ULOQ.” 
Section 4.
 
 • “All Randomized Subjects”, “Reactogenicity Set”, and “All-available Immunogenicity Set (mITT)” were added in Section 4.

Version/ date	Associated protocol	Summary and rationale for changes
		
Section 3.4:
 
 Updated definition of baseline for the primary non-inferiority test of the difference of SR in Part B Cohort 1 and 4 to align with the definition for the descriptive analysis of GMFR and SR. COVID-19 infection status at baseline and during surveillance are updated in Section 3.3.1 and 3.4. 
Section 5.2:
 
 Clarified analysis method for unadjusted GMR. 
Section 6.1.2:
 
 The propensity score method was replaced with random selection with matching factors sex and age (in years) to ensure comparable distribution in each cohort. 
Section 6.1.2.1, 6.1.2.2, 6.1.2.5, and 6.1.2.6
 
 Added sensitivity immunogenicity analyses for unadjusted GMR and difference of SR using Immunogenicity Analysis Per Protocol Set, mITT, and changed adjusted sensitivity analysis using Immunogenicity Analysis Set. 
Section 6.4 and 6.5:
 
 Diabetes was deleted from demographic table and subgroup analysis. Age group 18-55 vs 56-85 years was added for subgroup analysis. 
Section 6.6.1
 
 Summary of lab safety assessment at screening was changed to be based on All Randomized Subjects.
4/30 Jan 2024	Protocol V7.0, 28 Jun 2023	
Section 3.1.1.1
 
Updated the calculation of duration of reactogenicity event to “Duration will be calculated in days as the difference from the start of the first reported event to the resolution of the last reported event, inclusive. The resolution date for events lasting longer than 7 days was recorded in the subject’s adverse event case report form. If the resolution date is partial or missing, the duration will be considered unknown.”

Version/ date	Associated protocol	Summary and rationale for changes
		
Section 3.3.1 Updated definition of confirmed COVID-19 cases.
 
Section 3.3 Added exploratory endpoint CD4+ and CD8+ T-cell responses (Ex vivo ELISpot) for Part A with endpoint description in Section 3.3.3 and analysis in Section 6.3.1.2.
 
Section 3.4.1 Updated Definition of baseline value and SARS-CoV-2 infection at baseline and post vaccination
 
Section 4 Added the clarification regarding how to handle mis-dosed subjects into safety and immunogenicity analysis sets.
 
Section 6.1.1 Added “The summary analyses post dose 2 and post dose 3 of IMP will be performed with subjects who received two doses and three doses of IMP to calculate the percentages”.
 
Section 6.1.1.1 Added 6.1.1.1 Safety Overview.
 
Section 6.1.1.4, 6.1.1.5 Added number of events in the AE and SAE summary tables.
 
Section 6.1.2.1-4, 6.1.3.1-2 Remove sensitivity analyses using the Immunogenicity Analysis Per Protocol Set and All-available Immunogenicity Set (mITT).
 
Section 6.1.2.7 and Section 6.1.2.8 These two analyses will not be performed.
 
Section 6.3.1.1 Added CD4+ and CD8+ T-cell responses (Ex vivo ELISpot).
 
Section 6.4 and 6.5 Resume diabetes (yes and no) as subgroup factor in Part B and C.
 
Section 7.1 Updated based on the actual analysis conducted.
 
Section 8.1, 8.2 and 8.3 Updated Section 8.1 Additional analysis sets for immunogenicity analysis. Added Section 8.2 Changes in interim analysis Added Section 8.3 Withdrawal of primary objectives to demonstrate the non-inferiority of

Version/ date	Associated protocol	Summary and rationale for changes
		
immune response against VOC (B.1.1.7 and B.1.617.2) after two doses of multivalent vaccine BNT162b2 (B.1.1.7 + B.1.617.2) in terms of GMT and SR for COVID-19 vaccine-naïve subjects in Part B Cohort 6.

5/23 Feb 2024	Protocol V7.0, 28 Jun 2023	
Appendix 2 Added Appendix 2. Subject selection for primary and secondary immunogenicity analysis in Part B
 
Remove “At the time this risk assessment was authored” from Section 8.3.

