## Outcome

The investigator has to assess the outcome of an AE (and not the trial subject's outcome) at the time of documentation based on the following criteria:

- Recovered/resolved \* (= complete resolution of the AE)
- Recovering/resolving (= AEs which are improving but not yet resolved completely, e.g., decrease in an intensity grade)
- Not recovered/not resolved (= AEs which are ongoing without improving or still present when the trial subject deceases due to another cause)
- Recovered/resolved with sequelae \* (= trial subject recuperated but retained pathological conditions resulting from the AE; the sequelae should be indicated)
- Fatal \*\* (= death due to the AE)
- Unknown (e.g., in case the trial subject is lost to follow-up)

\* Generally, an AE is defined as recovered/resolved if all symptoms have ceased, no medication for treatment of the event is taken anymore and no other measures (e.g., hospitalization) are ongoing.

If the trial subject has developed permanent or chronic symptoms or if the event requires long term medication(s), the AE is defined as recovered/resolved with sequelae as soon as no changes of symptoms and/or medication(s) are expected anymore.

An AE that is documented as a worsening of a medical condition already known at baseline, is defined as recovered as soon as the medical condition has returned to baseline status.

\*\* In case of a fatal event, the event term should not be "death" but the underlying event which led to death (death = outcome). If there is more than one AE in a fatal case, only the AE leading to death will be attributed with the outcome "fatal". All other AEs ongoing at the time of death will be attributed with the outcome "not recovered/not resolved". A copy of an autopsy report should be submitted if available.

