3.1.1.1 Local reactions

The local reactions assessed by trial subjects and reported in the e-diary are pain at the injection site, tenderness, erythema/redness, induration/swelling, from Day 1 through Day 7 after each trial IMP dose, where Day 1 is the day of each IMP injection. A subject is deemed to have had a local reaction if they report the reaction as “yes” on any day of the e-diary recording period (i.e., Day 1 through Day 7 inclusive).

For redness and swelling, the reported size must be at least 2.5 cm (0.98 inches) to be deemed as a local reaction. Redness and swelling with a size less than 2.5 cm will not be included in the analysis.

Solicited local reactions will be categorized as mild, moderate, severe, or potentially life-threatening) and graded from 1 to 4, during the analysis as described in Table 5. The categories and grades are based on the FDA Guidance for Industry: [“Toxicity Grading Scale for Healthy Adult and Adolescent Volunteers Enrolled in Preventive Vaccine Clinical Trials”](#).

Table 5. Local reaction grading scale

	Mild (Grade 1)	Moderate (Grade 2)	Severe (Grade 3)	Potentially life-threatening (Grade 4)
Pain at the injection site	Does not interfere with activity	Interferes with activity	Prevents daily activity	Emergency room visit or hospitalization for severe pain
Tenderness	Mild discomfort to touch	Discomfort with movement	Significant discomfort at rest	Emergency room visit or hospitalization
Erythema /redness ^a	2.5 cm to 5.0 cm (0.98 in to 1.96 in)	>5.0 cm to 10.0 cm (>1.96 in to 3.94 in)	>10 cm (>3.94 in)	Necrosis or exfoliative dermatitis
Induration /swelling ^b	2.5 cm to 5.0 cm (0.98 in to 1.96 in)	>5.0 cm to 10.0 cm (>1.96 in to 3.94 in)	>10 cm (>3.94 in)	Necrosis

- a) In addition to grading the measured local reaction at the greatest single diameter, the measurement should be recorded as a continuous variable.
- b) Induration/swelling should be evaluated and graded using the functional scale as well as the actual measurement.

For subjects recording at least one local reaction from Day 1 through Day 7 after IMP injection:

- The maximum severity grade is equal to the highest graded local reaction within the recording period.

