- Duration will be calculated in days as the difference from the start of the first reported event to the resolution of the last reported event, inclusive. The resolution date for events lasting longer than 7 days was recorded in the subject's adverse event case report form. If the resolution date is partial or missing, the duration will be considered unknown.
- Onset day, defined as the first day of reporting any severity, will be derived for each recorded local reaction. If a subject report changes in severity of the local reaction, only the first day of reporting that specific local reaction will be counted. Local reaction onset day for Dose 1 will be calculated from the IMP Dose 1 injection date, for Dose 2 from the IMP Dose 2 date and for Dose 3 from the IMP Dose 3 date.

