3.1.1.2 Systemic events

Symptoms of systemic events assessed by trial subjects and recorded in the e-diary are fever, fatigue, headache, chills, vomiting, nausea, diarrhea, new or worsened muscle pain, and new or worsening joint pain from Day 1 through Day 7 inclusive, where Day 1 is the day of each IMP injection. The derivations for systemic events will be handled similar to the way local reactions are handled for presence of an event, severity level, duration, and onset day.

Fever is defined as an oral temperature $\geq 38.0^{\circ}\text{C}$ (100.4°F). Temperatures collected in degrees Fahrenheit will be converted to degrees Celsius using $(^{\circ}\text{F} - 32) \times 5/9$ and grading will be based on the unrounded conversions. An investigator or medically qualified person

must confirm a trial subject's fever as $>40.0^{\circ}\text{C}/>104.0^{\circ}\text{F}$ before it is entered in the trial database.

The highest oral temperature for each day will be recorded in the e-diary and the maximum temperature from Day 1 through Day 7 will be graded as described in [Table 6](#).

Solicited systemic events will be categorized as mild, moderate, severe, or potentially life-threatening) and graded from 1 to 4, during the analysis as described in [Table 6](#).

Table 6. Systemic events grading scale

	Mild (Grade 1)	Moderate (Grade 2)	Severe (Grade 3)	Potentially life-threatening (Grade 4)
Fever (oral temperature of $\geq 38.0^{\circ}\text{C}/\geq 100.4^{\circ}\text{F}$)	$\geq 38.0^{\circ}\text{C}/\geq 100.4^{\circ}\text{F}$ to $38.4^{\circ}\text{C}/101.1^{\circ}\text{F}$	$\geq 38.5^{\circ}\text{C}/\geq 101.2^{\circ}\text{F}$ to $38.9^{\circ}\text{C}/102.0^{\circ}\text{F}$	$\geq 39.0^{\circ}\text{C}/\geq 102.1^{\circ}\text{F}$ to $40.0^{\circ}\text{C}/104.0^{\circ}\text{F}$	$>40.0^{\circ}\text{C}/>104.0^{\circ}\text{F}$
Vomiting	1 to 2 times in 24 h	>2 times in 24 h	Requires intravenous hydration	Emergency room visit or hospitalization for hypotensive shock
Diarrhea	2 to 3 loose stools in 24 h	4 to 5 loose stools in 24 h	6 or more loose stools in 24 h	Emergency room visit or hospitalization for severe diarrhea
Headache	Does not interfere with activity	Some interference with activity	Prevents daily routine activity	Emergency room visit or hospitalization for severe headache
Fatigue/tiredness	Does not interfere with activity	Some interference with activity	Prevents daily routine activity	Emergency room visit or hospitalization for severe fatigue

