6.1.1.2 Local reactions

The number and percentage of subjects reporting local reactions (pain at the injection site, tenderness, erythema/redness, induration/swelling) within 7 days after each dose will be

summarized by maximum severity and cumulatively across severity levels. The associated 2-sided Clopper-Pearson 95% CI's will also be displayed.

The Reactogenicity Set will be used for local reaction summaries. Subjects without any e-diary data throughout the 7 days after vaccination or have recorded events only beyond 7 days, will be excluded from the local reaction analysis.

In addition, local reactions will also be summarized by:

- Duration (days) of each local reaction after each dose.
- Onset day of each local reaction after each dose.

Bar charts with the proportions of subjects for each local reaction throughout 7 days after each dose will be plotted. The bars will be divided into severity categories to highlight the proportions of subjects by maximum severity. In addition, listing of subjects in the Reactogenicity Set, with reported local reactions, will be provided.

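### Reaction durations without a complete end date are set to unknown, so some of the longest reactions can drop out of the duration summaries

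*SAP*

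**What the plan says.** SAP 3.1.1.1 defines the quantity as follows: "Duration will be calculated in days as the difference from the start of the first reported event to the resolution of the last reported event," counted inclusively and with no cap at Day 7. Presence, severity and onset through Day 7 come from the daily e-diary. Beyond that the source changes: "The resolution date for events lasting longer than 7 days was recorded in the subject's adverse event case report form". The rule at issue comes next: "If the resolution date is partial or missing, the duration will be considered unknown". The same sentence stands in the SAP version history for version 4 and in the operative text of 3.1.1.1, so it is current.

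For systemic events, SAP 3.1.1.2 says "The derivations for systemic events will be handled similar to the way local reactions are handled", and names duration among the derivations covered. The planned output in SAP 6.1.1.2 is "Duration (days) of each local reaction after each dose", and SAP 6.1.1.3 repeats it for systemic events. SAP 5.2.3 lists the statistics for a continuous variable: n, mean, median, standard deviation, minimum and maximum. SAP 5.3 imputes nothing beyond adverse event and medication dates. Its adverse event rules complete onset dates, to set the treatment-emergent flag, and do not supply resolution dates.

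The protocol allows an adverse event to end without a resolution date. One permitted outcome (Protocol 10.3.1.7, Outcome) is "Not recovered/not resolved (= AEs which are ongoing without improving or still present when the trial subject deceases due to another cause"), and another is unknown. Protocol 8.3.3 lets follow-up stop at stabilization or loss to follow-up, and lets the investigator confirm that no final status is available.

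**The concern.** The rule handles a right-censored duration as if it were simply missing. A reaction that is still present when the diary closes has a known minimum duration, and a partial end date (month and year, say) narrows it further. The rule uses neither.

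The chance of losing the duration can also depend on the duration itself. A reaction that ends inside the diary period can have its end read from the daily entries. One that continues needs a complete date on a separate form, and one that never resolves cannot have such a date. Reactions that fail to resolve are of particular interest in a reactogenicity profile, and they contribute nothing to the mean or maximum reported for their reaction type, dose and cohort.

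**Working it through.** There is no stated figure in the plan to reproduce. The check has two parts: what follows from the wording, and how large the effect could be under assumed rates.

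**What follows from the wording**

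1. An unresolved reaction has no resolution date, so its duration is always unknown. No assumed rate is needed for this.
2. A solicited reaction that starts on Days 1 to 7 and continues past Day 7 must be reported as an adverse event (Protocol 8.3, SAP 3.1.1.3). The database therefore shows that it was still present after Day 7.
3. If such a reaction began on Day k and was present on Day 8, its inclusive duration is at least 8 − k + 1 = 9 − k days: at least 8 days for onset on Day 1, at least 6 for onset on Day 3. The rule discards this bound.
4. A reaction past Day 7 with a complete date on the form keeps its full duration.

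**Illustrative size (all inputs assumed)**

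Let p be the share of reactions that run past Day 7, L their mean duration, and 2.5 days the mean of the others. Let m and s be the shares with unknown duration among the long and the short reactions.

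- True mean = (1 − p) × 2.5 + p × L
- Summarised mean = [(1 − p)(1 − s) × 2.5 + p(1 − m) × L] / [(1 − p)(1 − s) + p(1 − m)]

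For p = 5%, L = 14, m = 50%, s = 0: true mean = 0.95 × 2.5 + 0.05 × 14 = 3.075; summarised mean = (2.375 + 0.35) / (0.95 + 0.025) = 2.725 / 0.975 = 2.795.

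| p | L (days) | m | s | True mean | Summarised mean | Difference |
|---|---|---|---|---|---|---|
| 1% | 10 | 10% | 0 | 2.575 | 2.568 | −0.007 |
| 5% | 14 | 10% | 0 | 3.075 | 3.020 | −0.055 |
| 5% | 14 | 30% | 0 | 3.075 | 2.909 | −0.166 |
| 5% | 14 | 50% | 0 | 3.075 | 2.795 | −0.280 |
| 10% | 14 | 50% | 0 | 3.650 | 3.105 | −0.545 |
| 10% | 28 | 50% | 0 | 5.050 | 3.842 | −1.208 |
| 10% | 28 | 100% | 0 | 5.050 | 2.500 | −2.550 |
| 5% | 14 | 30% | 30% | 3.075 | 3.075 | 0 |
| 5% | 14 | 10% | 20% | 3.075 | 3.143 | +0.068 |

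With s = 0, p from 1% to 10%, L from 10 to 28 days and m from 10% to 50%, the shift in the mean runs from about −0.01 to −1.21 days. The last two rows show what happens when short reactions also lose dates: equal rates give no bias, and a higher rate among short reactions reverses the sign.

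**Median and maximum**

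If only long reactions drop out, the retained median is the true quantile at 0.5 × (1 − p × m). For p = 5%, m = 50% this is 0.4875. At the extreme, p = 10% and m = 100%, it is 0.45. With durations in whole days the median may not change at all. The maximum is understated whenever the longest reaction is the one without a date.

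**The case against.** The case for leaving the rule alone is substantial. The primary safety estimand is the percentage of subjects with a reaction up to 7 days after each dose. Duration is an additional descriptive summary with no test or decision rule. Undated reactions stay in the incidence, maximum severity and onset summaries. SAP 6.1.1.1 counts solicited events that continue past Day 7 whether or not they have an end date, and SAP 5.3 displays missing counts when any cohort has one. Protocol 10.3.1.7 requires an end date on the case report form and Protocol 8.3.3 requires follow-up, so a high rate of missing dates should not be presumed. Not imputing also fits the SAP's observed-case convention.

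Most of this stands, and it rules out several stronger readings that a reader might infer:

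- That the longest reactions drop out as a class. Only those without a complete date do.
- That durations are always biased short. This needs short reactions to lose no dates, yet the rule covers any reaction and a diary that stops early can leave a short one undated. The documents give no rates for either group.
- That the median is pulled down materially. It is not.
- That the reported share lasting over 7 days is cut. With p = 5% and m = 50%, the share among known durations would be 0.025 / 0.975 = 2.6% in place of 5%, but the SAP does not plan that statistic.

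What the objection does not answer is the loss of known information. The SAP 6.1.1.1 count pools reactions continuing past Day 7 with events starting after Day 7 and with serious events, and it corrects no reaction's duration summary. A bare missing count does not show which of the missing values are known to be long. Censoring at the last known day is not imputation, so the observed-case convention is no bar to it.

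**Conclusion.** The point holds as a risk in a descriptive safety summary. By the wording alone, a reaction that never resolves always has an unknown duration, even where the adverse event record shows that it continued past Day 7. The mean and maximum durations per reaction, dose and cohort may therefore be understated, while the median is little affected.

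The size cannot be fixed from the documents. If undated reactions are confined to those past Day 7, the assumed range gives a shift in the mean of about −0.01 to −1.21 days for 10% to 50% undated. If short reactions lose dates as well, the shift can vanish or change sign. No hypothesis test, sample size, power figure or primary percentage is touched.

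**What to change.** In SAP 3.1.1.1, replace the unknown-duration sentence with a rule that a reaction with a partial or missing resolution date is right-censored at the last day it is known to be present, using whatever bound a partial date gives. Apply it to systemic events through 3.1.1.2.

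In SAP 6.1.1.2 and 6.1.1.3, for each reaction, dose and cohort:

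- add a past-Day-7 row (more than 7 days after injection) that includes every reaction reported as continuing past Day 7, with or without an end date;
- show the number of unknown durations, split by whether the reaction was ongoing after Day 7;
- label the mean and maximum as based on complete durations, and mark the maximum as a lower bound where a censored reaction could exceed it.

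A Kaplan-Meier median is an optional sensitivity summary. A full set of duration bins is not advisable, because a reaction last known on Day 3 with no end date fits none of them.

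SAP 5 limits reactogenicity tables, figures and listings to events within 7 days of injection, while 3.1.1.1 measures duration beyond that. The SAP should say whether the limit governs which reactions enter or also where duration stops.

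The cost is minor programming and one extra table row, using data already collected. Censoring cannot recover an end date or a maximum that was never observed.
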